**c) Proposed Start Date (may not precede IRB approval date):**

August 1, 2015

2.

Study Procedures (If this is a student project, the methods section of the thesis or dissertation proposal must be attached in section #16 - Attachment section.)

**a) In lay language, describe all the procedures, from screening through end-of-study, that the human subject must undergo in the research project, including study visits, drug treatments, randomization and the procedures that are part of standard of care. Please note: Do NOT respond "See Attachment Section." If you would like to add tables, charts, etc., attach those files in the Attachment section (#16).**

Study Overview:

Pre-diabetic and healthy participants will first undergo a medical questionnaire, resting ECG, graded exercise test with ECG and assessment of VO2max, anthropometric measurement (height, weight and body composition by DEXA scanning), an oral glucose tolerance test (OGTT), and a muscle biopsy.

Prediabetic participants will be screened to eliminate those lactose intolerant, medications known to affect the primary outcomes, medications or recent procedures contraindicated with metformin or not pre-diabetic. Subjects who meet these criteria will be randomized so that subject characteristics are matched between groups, while the study team and participants will remain blinded to treatment (i.e., randomized, double-blind study design). Subjects will be assigned to exercise + carbohydrate + placebo, exercise + protein + placebo, exercise + carbohydrate + metformin, or exercise + protein + metformin.

A minimum of two days apart from the VO2max test, skeletal muscle will be sampled from pre-diabetic and healthy participants. During these visits, pre-diabetic subjects will have the option to participate in a study to test the impact of one counseling session on physical activity after completion of the exercise training and to identify individual, socio-cultural and environmental determinants of physical activity 12 weeks after the end of the exercise intervention. If the subjects wish to participate they will complete questionnaires to measure sociodemographic information, physical activity, self-efficacy, planning, self-regulation and outcome expectancy of exercise, and perceptions of neighborhood support at baseline, completion of exercise training and 12 weeks after the exercise training.

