**\*\*\* Subject Population (a-g) \*\*\***

8. Subject Population - In the space below, please detail the participants that you are requesting to recruit (include requested participant number and description of each group requested). (Input N/A if not applicable)
- a) **Requested Participant Description (Include number of participants that you plan to study and description of each group requested, if applicable).**

We plan to recruit 120 men and women with an estimation that 15-25% of participants will not qualify (i.e., screen out) and 15-25% of participants will not complete the study (i.e. drop out). We plan to complete the study in 60 men and women aged >55 years who are prediabetic defined as impaired fasting glucose (100 to 126 mg/dl), HbA1c (5.7-6.4%), family history of type 2 diabetes, and/or impaired glucose tolerance defined as 2 hour postprandial blood glucose of 140 to 200 mg/dl. Participants will be eligible if they meet any 1 of these criteria.

10 healthy individuals, 18-45 years old who have normal glucose values (fasting glucose (<100mg/dl), HbA1c (<5.7%), 2 hour postprandial blood glucose (<140mg/dl)) or no family history of type 2 diabetes will be recruited.

Sub-study: 20 pre diabetic participants and 10 healthy individuals will complete the study.  
Subpopulation of [xx] participants will be recruited for Physical Activity Behavior Counseling (previously approved in Amendment 3.

- b) **What is the rationale for studying the requested group(s) of participants?**

Individuals at risk for T2D are the intended population for metformin; CGM; and Counseling studies. We will use a healthy control group to compare to individuals at risk for T2D.

- c) **If applicable, state the rationale for involvement of potentially vulnerable subjects to be entered into the study, including minors, pregnant women, economically and educationally disadvantaged, or decisionally impaired subjects. Specify the measures being taken to minimize the risks and the chance of harm to the potentially vulnerable subjects.**

We will not enroll minors, pregnant women, economically and educationally disadvantaged, or decisionally impaired subjects.

- d) **If women, minorities, or minors are not included, a clear compelling rationale must be provided. Examples for not including minors: disease does not occur in children; drug or device would interfere with normal growth and development; etc.**

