**Statistical Plan**

Data are presented as mean  $\pm$  standard error of the mean (SEM) and a significance was set a priori at  $P < 0.05$ . Normality was confirmed by the D'Agostino and Pearson test. A two-way ANOVA (Treatment Group x Time) with repeated measures for time was performed. Upon a significant effect, a Holm-Sidak's post-hoc test was used for multiple comparisons. When comparing the change ( $\Delta$ ) from pre to post-intervention between groups, data were analyzed using an unpaired t-test. Pearson's correlation coefficient ( $r$ ) was used to determine associations between dependent variables. GraphPad Prism 7.0 was used to perform statistical analysis

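### Allocation is described as matched on subject characteristics, but the planned tests contain only group and time. Where those characteristics drove allocation and predict the outcome, the tests are conservative and precision is lost.

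*Combined protocol and SAP*

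**What the plan says.** The Study Overview in Study Procedures (item 2a) says eligible prediabetic subjects are "randomized so that subject characteristics are matched between groups" and then assigned to one of four arms. It does not name the characteristics, or say whether balance comes from stratification, minimisation or pairing.

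The Statistical Plan is one paragraph. On the main model it says: "A two-way ANOVA (Treatment Group x Time) with repeated measures for time was performed". Holm-Sidak comparisons follow a significant effect. For the change from before to after the intervention, "data were analyzed using an unpaired t-test". The threshold is 0.05, with sidedness not stated. No covariate, stratum, matching factor or baseline adjustment appears in any of these tests.

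On size, Subject Population (item 8a) says "We plan to complete the study in 60 men and women aged >55 years" and "We plan to recruit 120 men and women", with 15-25% expected to be screened out and 15-25% expected to drop out. No power, effect size or standard deviation is given. The Study Overview also says isotope incorporation, which measures protein synthesis, is obtained after training only.

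**The concern.** When allocation forces arms to be alike on a characteristic, that characteristic contributes less to the chance difference between arms than it would under simple randomisation. A test with no term for it still counts its full contribution as residual noise. If the characteristic predicts what is being analysed, the reported standard error is too large, the interval too wide and the p-value too high.

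At stake is precision in a small trial: 60 completers over four arms is 15 per arm if allocation is equal. A real effect could be missed although information already collected would have helped to show it. The point matters most for comparisons of level between arms. The post-only isotope outcome is one of these, because it has no baseline value to absorb differences between people.

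**Working it through.** **Inputs from the documents.** 120 recruited, 60 completing, four arms, 15-25% screen failure, 15-25% dropout, alpha 0.05.

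**Assumed, because the documents are silent.** Equal allocation, two-sided tests, dropout at random, and R² (the share of outcome variance explained by the characteristic) between 0.2 and 0.5.

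**The plan's own figure.** There is no power calculation to reproduce. The recruitment figures fit at the pessimistic end: 120 − 0.25×120 − 0.25×120 = 60. With 25% dropout, 60 completers need 60/0.75 = 80 randomised, which is 20 per arm with 15 completing.

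**Step 1: formula.** With n completers per arm and outcome variance σ², the unadjusted t-test reports a variance of about 2σ²/n for a two-arm difference. Let f be the share of the characteristic's variance that allocation balances, and r the share of randomised subjects who complete. Random dropout undoes part of the balance, because 15 drawn from a balanced 20 still carry (1 − 15/20) of the original sampling variance. So:

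- true variance ≈ (2σ²/n)(1 − r·f·R²)
- reported SE / true SE ≈ 1/√(1 − r·f·R²)
- actual type I error ≈ 2·P(t₂₈ > 2.048 × that ratio)

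**Step 2: numbers, with r = 0.75.** For tight matching f = 1. For a median split of a normally distributed characteristic f = 2/π = 0.637.

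| Scheme | R² | SE ratio | Type I error |
|---|---|---|---|
| Simple randomisation (f = 0) | any | 1.00 | 5.0% |
| Median-split strata | 0.2 | 1/√(1 − 0.0955) = 1.05 | 4.0% |
| Median-split strata | 0.5 | 1/√(1 − 0.239) = 1.15 | 2.6% |
| Tight matching | 0.2 | 1/√(1 − 0.15) = 1.08 | 3.5% |
| Tight matching | 0.5 | 1/√(1 − 0.375) = 1.26 | 1.5% |

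Simulation of the four-arm design (80 randomised, 60 completing, two arms compared) gave overstatement of about 3-14% for strata, with type I error about 4.5% to 2.5%. For tight matching it gave about 8-25%, with type I error about 3.5% to 1.6%. The formula agrees to within about two percentage points on the standard error. The low end of the stratified case is the least certain.

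**Step 3: ceiling.** Exact pairing without dropout (r = f = 1) gives 1/√0.8 = 1.12, 1/√0.7 = 1.20 and 1/√0.5 = 1.41 at R² of 0.2, 0.3 and 0.5.

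**Step 4: level or change.** Simulation, 15 v 15, tight matching, no dropout:

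- Characteristic explains half the variance of level and none of change, analysed as change: reported SE 0.280, true 0.279, type I error 4.7%.
- The same characteristic, post-only outcome: reported 0.365, true 0.262, type I error 0.9%.
- Characteristic also explains 25% of the variance of change, analysed as change: reported 0.325, true 0.283, type I error 2.5%.

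**Step 5: power.** Simulation, 15 v 15, no dropout, with a standardised effect of 1.02, chosen to give about 80% unadjusted power. R² refers to the quantity analysed.

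| R² | Tight matching: unadjusted v adjusted | Simple randomisation: unadjusted v adjusted |
|---|---|---|
| 0 | 77.5% v 77.4% | 78% v 76% |
| 0.1 | 79% v 82% | 77% v 80% |
| 0.25 | 80% v 88% | 77% v 86% |
| 0.5 | 85% v 97% | 77% v 96% |

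Adjustment for a predictive characteristic therefore gains power under either scheme. A useless covariate costs at most about two points here.

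**The case against.** The strongest reply is that the mechanism rests on one phrase in a form field that asks for lay language. The phrase may only describe what randomisation is expected to achieve. If allocation was simple, the unadjusted standard error is valid: at R² = 0.5 the simulation gave 0.361 reported against 0.365 true. The Attachments list a GCP protocol that is not available here and may describe the method. This stands, and it makes the standard-error part of the point conditional. It does not remove the benefit of adjusting for a predictive characteristic, and the two sections still need to agree.

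Second, the quoted tests largely use each person as their own control. In the change t-test and the group-by-time term, a characteristic that predicts only level cancels. This also stands. Only predictors of change matter there, and the documents give no R² for any.

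Third, the post-only isotope outcome is not clearly covered by either quoted test. One needs repeated time points and the other a pre-to-post change. The documents do not show that it will be analysed without adjustment; they do not say how it will be analysed.

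Fourth, the error is conservative, so it cannot produce a false positive. That is correct and limits the severity.

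A reader might infer that all the trial's standard errors are too large, by 12-41%, and that its 5% tests run far below 5%. The documents do not support this. The figure needs exact pairing on one strong predictor with no dropout, whereas the plan names no matching method and expects 15-25% to drop out.

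**Conclusion.** The point holds conditionally. The mismatch between sections is plain in the text: allocation is described as matched, and no analysis has a term for the matched characteristics or for baseline. An error in the standard error follows only if allocation really was constrained and the characteristics predict the quantity analysed.

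Under the stated assumptions (R² 0.2-0.5, equal allocation to four arms, 80 randomised, 60 completing) the overstatement is about 3-14% with median-split strata and about 8-25% with tight matching. It is nil under simple randomisation or for unrelated characteristics, and little or nothing for change scores when only level is predicted. Without R², a standard deviation or a power calculation, the loss in this trial cannot be reduced to one figure. The consequence is lost precision, with no inflation of false positives. The remedy is cheap enough to be worth making in any case.

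**What to change.** 1. In the Statistical Plan, replace the unpaired t-test on change with a linear model (ANCOVA) of the post-intervention value on treatment group, the baseline value and the few pre-specified characteristics used in allocation.
2. Include the same allocation factors in the repeated-measures model, and in whatever between-arm model is specified for the post-only isotope outcome.
3. In Study Procedures (item 2a), name those characteristics and the method that balances them, so that the two sections agree. If allocation was simple randomisation, say so and drop the reference to matching. A small pre-specified set of prognostic covariates would still be worthwhile.
4. Keep the list short. With about 15 per arm, a long or open-ended set of covariates would use up the gain.

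The cost is SAP wording and a few degrees of freedom. No new data are needed.

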**1. Purpose of the study**

- a) Provide a brief lay summary of the project in <200 words. The lay summary should be readily understandable to the general public, and is, for example, what would be released to a newspaper if requested.

We propose that post-exercise milk protein feeding will enhance the mitochondrial protein synthesis (biogenesis) response to an exercise-training program. In addition, we propose that this stimulatory effect of protein feeding will overcome the potential blunting effect of metformin on exercise responses. We will investigate these outcomes over a 12-week exercise-training program in older adults with pre-diabetes with or without metformin treatment.

Sub-study:

- 1. CGM in Individuals with prediabetes undergoing an exercise-training program with or without Metformin.
- 2. CGM in healthy control individuals to compare to individuals with prediabetes.

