**b) What does the Investigator(s) hope to learn from the study?**

We hope to:

- a) provide the first evidence that post-exercise milk protein supplementation is effective in diseased population (i.e., older adults with pre-diabetes) and those on medications (i.e., metformin).
- b) demonstrate that the potential inhibitory effects of metformin on aerobic exercise adaptations can be opposed by milk protein feeding.

Sub-study

1. Glucose Profiles via CGM in pre diabetic individuals before, during and after the intervention (i.e., aerobic exercise training with or without metformin with post-exercise carbohydrate or carbohydrate+protein feeding as listed below in 2a).
- 2: Glucose profiles via CGM in healthy individuals. Healthy individuals will complete baseline procedures but will not complete an intervention.

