Pre diabetic and healthy participants will also have the option to participate in a study to wear a Dexcom generation 6 (G6) continuous glucose monitor (CGM) to measure glucose values every 5 minutes. Healthy participants will wear the device once for up to 10 consecutive days. Pre-diabetic participants will wear the device for up to 10-consecutive days at three different time points: before, during and after the 12-week exercise intervention for a total of 30 days wearing the CGM. The Dexcom G6 CGM is for investigational use only and is not FDA approved. The G6 is modeled after commercially available, FDA approved CGM devices. The differences between the G6 and commercially available devices are a reduced calibration scheme, meaning less finger stick blood glucose measurements for calibration; a longer wear for up to 10 days for the G6 vs. 7 days for commercially available product. Last, commercially available devices could give false high glucose readings if individuals took acetaminophen. The G6 sensor contains updated sensor technology aimed to block the interference of acetaminophen.

After randomization into placebo or metformin groups, the pre-diabetic subjects will begin a 12-wk exercise

intervention consisting of 3 days per week of aerobic exercise training with post-exercise consumption of a 20 gram protein beverage or isocaloric carbohydrate beverage. We have completed this supplementation protocol in previous studies and a currently ongoing investigation.

At the 8-wk time point, pre-diabetic subjects will begin the daily consumption of heavy water (D2O) for the assessment of mitochondrial and individual protein synthesis. At the completion of the training period, the pre-diabetic subjects will repeat all assessments performed prior to training including the DEXA, VO2max, OGTT and muscle sample. Muscle samples obtained pre- and post-training will be used to evaluate mitochondrial function using high-resolution respirometry, western blot analysis, and stable isotope incorporation (post only).

Healthy participants will complete the medical history questionnaire, resting ECG, graded exercise testing (ECG and VO2max), DEXA, OGTT, CGM, and muscle biopsy.

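### Mitochondrial protein synthesis is measured only after training, so neither group comparison in the supplied Statistical Plan can be run on it; a post-value protein x metformin model with listed contrasts is needed

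*Combined protocol and SAP*

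**What the plan says.** Section 1, Purpose of the study, item a, puts forward that "post-exercise milk protein feeding will enhance the mitochondrial protein synthesis (biogenesis) response to an exercise-training program". Item b adds two aims. The first is to show that supplementation is "effective in diseased population (i.e., older adults with pre-diabetes) and those on medications (i.e., metformin"). The second is to "demonstrate that the potential inhibitory effects of metformin on aerobic exercise adaptations can be opposed by milk protein feeding".

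Section 2a, Study Overview, assigns participants with pre-diabetes to four arms: carbohydrate or protein, each with placebo or metformin. On allocation it says: "Subjects who meet these criteria will be randomized so that subject characteristics are matched between groups". The characteristics are not named. Heavy water starts at week 8 and serves to measure mitochondrial and individual protein synthesis. The pre- and post-training muscle samples are to be evaluated "using high-resolution respirometry, western blot analysis, and stable isotope incorporation (post only"). Under Skeletal Muscle Biopsy there are two samples, one before and one after training. Under Stable Isotope Labeling, heavy water is taken only in the last four of the 12 weeks.

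The Statistical Plan compares groups in two ways. First: "A two-way ANOVA (Treatment Group x Time) with repeated measures for time was performed". Second, for the change "from pre to post-intervention between groups, data were analyzed using an unpaired t-test". Multiplicity is handled in one sentence: "Upon a significant effect, a Holm-Sidak's post-hoc test was used for multiple comparisons". Pearson correlation is also listed, but it relates variables to each other and does not compare arms.

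**The concern.** A repeated-measures analysis over time and a change score each need at least two measurements per person, and isotope-based synthesis has one. The stated analysis therefore cannot be carried out on the one specific outcome that the hypothesis names.

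An analyst would have to choose a model, covariates and contrasts that the supplied plan does not state, possibly with results in hand. The choice matters because the aims ask different questions: whether protein raises synthesis overall, whether it helps people on metformin, and whether it makes good what metformin takes away. One contrast does not answer all three, and a convenient choice could be read as answering a question it does not address.

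**Working it through.** **Inputs.** Four arms (Study Overview). 60 planned completers (section 8a). Alpha 0.05 (Statistical Plan). Three assumptions: equal allocation, so 60 / 4 = 15 per arm; two-sided tests; no covariates. The documents give no SD or effect size for synthesis, so effects are in between-subject SD units. There is no figure in the plan to reproduce.

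**Step 1: can the stated comparisons be run?** With G = 4 groups, N = 60 and T time points, the degrees of freedom are:

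| Term | Formula | T = 2 | T = 1 (synthesis) |
|---|---|---|---|
| Group | G − 1 | 3 | 3 |
| Time | T − 1 | 1 | 0 |
| Group x Time | (G − 1)(T − 1) | 3 | 0 |
| Subjects within group | N − G | 56 | 56 |
| Within-subject residual | (N − G)(T − 1) | 56 | 0 |

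With T = 1 the time and interaction tests do not exist. The change score is undefined because the first biopsy comes before any labelling. Holm-Sidak follows a significant effect in that ANOVA, so it is not reached. Result: 0 of 2 comparisons. What remains estimable is a between-arm model on the post value, with 3 group df and 56 error df.

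**Step 2: precision of a post-value 2x2 model.** Half-width = t(0.975, 56) x SE, with t = 2.003:

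- Protein main effect (30 v 30): SE = √(2/30) = 0.258; half-width 0.52 SD.
- Any pairwise contrast (15 v 15): SE = √(2/15) = 0.365; half-width 0.73 SD.
- Protein x metformin interaction: SE = √(4/15) = 0.516; half-width 1.03 SD.

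**Step 3: which contrasts bear on item b's second aim?** Suppose protein adds 1.041 SD with or without metformin. That size is chosen only because it gives a pairwise contrast 80% power. Let metformin lower synthesis by 0, 1.041 or 2.0 SD. The share of trials in which each test rejects at 0.05 is:

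| Contrast | No deficit | Fully offset (1.041) | About half offset (2.0) |
|---|---|---|---|
| Protein main effect | 98% | 98% | 98% |
| Protein v carbohydrate, within metformin | 80% | 80% | 80% |
| Protein x metformin interaction | 5% | 5% | 5% |
| Metformin v placebo, within carbohydrate | 5% | 80% | >99% |
| Protein+metformin v carbohydrate+placebo | 80% | 5% | 73% |

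The first three rows do not change across the columns, so they cannot tell an absent deficit from a fully or half recovered one. The last two rows together can. These are general properties of a 2x2 design and show which contrast answers which question. They do not predict this trial's power.

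**Step 4: multiplicity.** If the main effect, the within-metformin contrast and the interaction were each tested at 0.05, the chance of at least one false positive when nothing differs is about 11% (simulation, 400,000 replicates). The contrasts therefore need an order or an adjustment.

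**The case against.** The strongest reply is that the adaptation is obvious: with one time point the group part of the ANOVA becomes a one-way comparison of post values, and a one-paragraph plan need not spell that out. This is fair as to feasibility, but the supplied plan does not state such a test, and a four-group test would not by itself separate the protein, metformin and interaction questions.

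Second, the importance of synthesis rests on a lay summary. Primary outcomes are mentioned in the Study Overview and the exclusion criteria but never named. That stands. A reader might infer that the trial's primary outcome has no analysis; the documents do not support that. Nor do they support saying that no suitable analysis exists anywhere, because Attachments lists a GCP protocol that is not shown.

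Third, the Statistical Plan is in the past tense and reads like a report of completed work, so additions may no longer be prospective. That also stands, and it affects how they must be labelled.

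Fourth, the lack of a protein x metformin term is not peculiar to synthesis: the plan has none for any outcome. That is true, but for outcomes measured twice the stated tests can at least be run.

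Two further readings go too far. One is that the synthesis data are unusable: the arms are randomised, so post-training differences compare them validly. The other is that the trial is underpowered for synthesis: without an SD or a target effect, the documents cannot show that.

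**Conclusion.** The point holds as a mismatch between measurement and analysis. Both stated group comparisons require a pre-training value that the design does not produce for isotope-based synthesis. This follows from the documents alone and needs no assumption. Respirometry, western blot, VO2max and other outcomes measured before and after training are not touched by it.

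The interval widths are secondary. They rest on 15 completers per arm, a common SD and no covariates.

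One limit remains under any analysis. Every arm trains and there is no pre value, so synthesis can show differences between arms but not that training itself raised it. It should be corrected; it does not undermine the design.

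**What to change.** In the Statistical Plan:

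- Restrict the Group x Time ANOVA and the change-score t-test to outcomes with pre and post values.
- Analyse synthesis with a linear model on the post-training value, with protein, metformin and protein x metformin terms. Adjust for the characteristics used to match groups at randomisation, listed by name.
- List these contrasts:
  1. The protein main effect, for the hypothesis in item a of Purpose. Name it the lead test.
  2. Protein v carbohydrate within the metformin arms, for the first aim in item b. It shows benefit in people on metformin, not offset.
  3. For the second aim in item b: metformin v placebo within the carbohydrate arms, to show whether there is a deficit, together with the estimate and 95% CI of protein+metformin v carbohydrate+placebo, to show how much is recovered. A non-significant difference there is not proof of full offset.
  4. The protein x metformin interaction, reported as whether protein changes the metformin effect.
- Apply Holm-Sidak across the listed contrasts other than the lead test.
- Report synthesis as between-arm differences over the last four weeks of training, not as a training-induced change.
- If synthesis results have already been seen, label these analyses post hoc and report all of them.

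The cost is a few sentences, with no new visits or samples. The downside is wide intervals: at about ±1.03 SD, a null interaction would be inconclusive, and the Holm-Sidak step makes contrasts 2 to 4 harder to declare significant.
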